[2] During the treatment period (both 2-week accommodation periods and 8-week Treatment phases), a second Piccolo POCT is performed promptly before dialysis end and within 30 minutes prior to rinse back on Mondays or Tuesdays after each long dialysis weekend (i.e., weekly), to measure K+, Ca++ and PO4.

[3] Applies only to the first twenty-five (25) patients randomized receiving standard treatment (hemodialysis using 2.0K+/2.5 Ca++ dialysate bath, without Lokelma supplementation) during Treatment Phase-1. Performed weekly, on Mondays or Tuesdays after each long dialysis weekend, promptly before dialysis end and within 30 minutes prior to rinse back.

[4] Performed weekly, on Mondays or Tuesdays after each long dialysis weekend, promptly before dialysis end and within 30 minutes prior to rinse back. Mg++ levels will be determined by the local laboratory at each site.

[5] Performed (if possible) upon symptomatic muscle cramping, promptly before dialysis end and within 30 minutes prior to rinse back. Mg++ levels will be determined by the local laboratory at each site.

[6] Baseline/Randomization is conducted on Week 1 of the new Dialysate Accommodation Period 1. Crossover occurs on the same day as Week 11 of the new Dialysate Accommodate Period 2. Neither Baseline/Randomization nor Crossover will be considered a separate visit.

[7] If ILR insertion is performed more than 30 days after the last K+ Piccolo POCT determination, please contact the sponsor who will determine if an additional K+ Piccolo POCT determination will be required prior to the baseline visit. These will be handled on a case-by-case basis.

[8] Adverse events will be collected from the time of first dose of Lokelmaâ, throughout the treatment and post-treatment follow-up period, up to the last study visit.

[9] SAEs will be reported from the time the patient signed the Informed Consent Form.

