## 7.2 Dose and Treatment Regimens

### 7.2.1 Dosing Regimen

Patients will take Lokelma supplementation on off-dialysis days (4 days/week) while receiving hemodialysis with 3.0 K+/2.5 Ca++ mEq dialysate bath (8-week treatment phase):

- Patients on a Monday-Wednesday-Friday dialysis schedule will take the study drug on Tuesday, Thursday, Saturday, and Sunday
- Patients on a Tuesday-Thursday-Saturday dialysis schedule will take the study drug on Monday, Wednesday, Friday, and Sunday.

The individual starting dose will be 5.0 grams (4 days/week), and will be titrated weekly in 5.0 gram increments up to a maximum of 15.0 grams (4 days/week) to maintain K+ within the desired target range (between 4.0 and 5.5 mEq/L):

- Patients who fail to achieve a pre-dialysis K+ of  $\leq 5.5$  mEq/L after one week of 5.0 grams Lokelma will be treated with 10.0 grams on off-dialysis days for an additional 7 days.
- Patients failing to achieve a pre-dialysis K+ of  $\leq 5.5$  mEq/L after one week of 10.0 grams Lokelma will have their study drug dose increased to 15.0 grams.
- Patients failing to achieve the target K+ after a 7-day course of 15.0 grams Lokelma on off-dialysis days will be considered a treatment failure and withdrawn from the study.

Potassium levels will be regularly monitored throughout the 8-week treatment phase, and the study drug dose adjusted based on the potassium levels (i.e., increased [up to a maximum of 15.0 grams/day] if potassium is  $>5.5$  mEq/L, or decreased if potassium is  $<4.0$  mEq/L).

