#### **8.5.6 Safety Analyses**

Lokelma-induced hypokalemia will be evaluated based on the total number of hypokalemic events defined as PiccoloPOCT or laboratory-measured K+ of < 3.5 mEq/L.

The incidence of dialysis-related hypokalemia, hypomagnesemia, hypophosphatemia, and low calcium will be evaluated based on the number of events promptly prior to the termination of dialysis where a PiccoloPOCT measurement of K+ is < 2.0 mEq/L OR Ca++ is < 7.0 mEq/L, OR Mg++ is < 2.0 mg/dl, OR a PO4 level is < 3.0 mEq/L. All episodes where a specific electrolyte falls below the above listed threshold will be considered an “event” for that electrolyte. The total number of “events” will be recorded during the 8-week Treatment Phase-1 and the 8-week Treatment Phase-2 cross-over periods and compared between the treatments.

Safety will also be assessed in terms of the frequency of AEs, SAEs, and withdrawals due to AEs, with focus on treatment-related events. Appropriate summaries of these data will be presented by treatment group and/or study period.

Adverse events will be coded using the Medical Dictionary for Regulatory Activities (MedDRA) system organ class (SOC) and preferred term (PT). A treatment-emergent AE

(TEAE) is defined as an AE with the start date on or after the first dose date and up to (and including) 14 days after the last dose date in each of study periods when patients received 3K Bath with Lokelma. However, when patients received 2K Bath without Lokelma, A treatment-emergent AE (TEAE) is defined as an AE with the start date on or after the first visit date and up to (and including) 14 days after the last visit date in each of study periods. Only TEAEs will be included in table summaries.

The number and percentage of participants experiencing AEs, SAEs, AEs that led to withdrawal, AEs that led to death, and the number of such events, will be summarised by SOC, PT, and treatment group and study period. The number and percentage of participants experiencing AEs will further be summarised by intensity and will be presented with the number of events at each level of intensity.

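### The 3.0 K TEAE window opens at the first Lokelma dose, so the first dialysis session on that bath is never in it, while the 2.0 K window opens at the first visit

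*Protocol*

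**What the plan says.** Section 8.5.6 gives two definitions of a treatment-emergent adverse event.

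- **3.0 K bath with Lokelma:** "TEAE) is defined as an AE with the start date on or after the first dose date", running "up to (and including) 14 days after the last dose date in each of study periods when patients received 3K Bath with Lokelma".
- **2.0 K bath:** the event starts "on or after the first visit date and up to (and including) 14 days after the last visit date".

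The section adds: "Only TEAEs will be included in table summaries".

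Two other places fix the calendar. Section 7.2.1 says "Patients will take Lokelma supplementation on off-dialysis days (4 days/week) while receiving hemodialysis with" the 3.0 K bath, and it lists dosing weekdays that exclude every dialysis day on both weekly schedules. Table 1 puts the Week 1 and Week 11 visits (Days 1 and 71) on the Monday or Tuesday after the long weekend, and its footnote 6 says "Crossover occurs on the same day as Week 11 of the new Dialysate Accommodate Period 2". Section 4.2 has patients move to the assigned bath once the post-insertion blanking period ends.

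**The concern.** The experimental treatment is the 3.0 K bath together with Lokelma. Exposure begins when the bath is changed, at a dialysis session, and the first packet cannot be taken until a later day. A window tied to the first dose therefore opens after exposure has begun, and only on the experimental side.

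Safety Objective #3 compares the two treatments on the frequency of adverse events, and the summary tables are where that comparison is made. The session that drops out is the first contact with the new bath, after the long interval. The protocol's own background (1.1.1) reports the highest atrial fibrillation rates during dialysis and raised rates for up to 12 hours afterwards. Loop-recorder data from the accommodation weeks are not analysed (4.2.2), and electrolyte events are counted over the 8-week phases. The adverse-event tables are thus the main comparative safety summary that covers the switch.

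**Working it through.** The plan states no figure to reproduce. The check applies the two definitions to the Table 1 calendar, day by day. Sequences are named by their order, because Table 4 and section 3.5 label A and B the opposite way round.

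**Inputs**
- Three sessions per week (3.1) and ten weeks on each bath (Days 1–70 and 71–140, Table 1): 10 × 3 = 30 sessions per period.
- Visits are weekly, each on the Monday or Tuesday. The last visit of the first period is Week 10: Day 15 + 7 × 7 = Day 64. In the second period it is Day 85 + 49 = Day 134.
- Dosing days are Tue/Thu/Sat/Sun on a Mon-Wed-Fri schedule and Mon/Wed/Fri/Sun on a Tue-Thu-Sat schedule (7.2.1).

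**Step 1: earliest dose.** On Mon-Wed-Fri, Day 1 is a Monday and the first dosing day is Tuesday, Day 2. On Tue-Thu-Sat, Day 1 is a Tuesday and the first dosing day is Wednesday, Day 2. The same count from Day 71 gives Day 72. The last possible dose is Day 70 or Day 140 on both schedules.

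**Step 2: windows as written**

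| Bath | Period | Opens | Closes | Own-bath sessions inside |
|---|---|---|---|---|
| 3.0 K | first | Day 2 | 70 + 14 = Day 84 | 29 of 30 |
| 3.0 K | second | Day 72 | 140 + 14 = Day 154 | 29 of 30 |
| 2.0 K | first | Day 1 | 64 + 14 = Day 78 | 30 of 30 |
| 2.0 K | second | Day 71 | 134 + 14 = Day 148 | 30 of 30 |

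The loss is 1/30 = 3.3% of sessions in each 3.0 K period, in up to 88 patients.

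**Step 3: where a switch-day event goes**
- 3.0 K first, event on Day 1: before Day 2, so in no window.
- 2.0 K first, event on Day 71: before Day 72, so not in the 3.0 K window, but not after Day 78, so in the 2.0 K window only. This affects up to 44 patients. If the words about each study period are read as cutting the tail at Day 70, the event is in no window.
- 3.0 K first, event on Day 71 (the first 2.0 K session): inside the 2.0 K window, and also inside the 3.0 K tail to Day 84.

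**Step 4: no dose taken.** Safety Set membership is settled in the first period (8.3.3), and visits continue after Lokelma is stopped (3.9). A patient who starts on 2.0 K and takes no Lokelma after cross-over stays in the set but has no first dose date, hence no 3.0 K window.

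**Step 5: tails.** The 3.0 K window lasts 84 − 2 + 1 = 83 days and the 2.0 K window 78 days. At cross-over the 3.0 K tail covers Days 71–84 on the 2.0 K bath (14 days, 6 sessions). The 2.0 K tail covers Days 71–78 on the 3.0 K bath (8 days, 4 sessions).

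**Step 6: after the change.** With both windows opened at the first session on the assigned bath, 30 of 30 sessions fall in their own window on both baths.

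**The case against.** **The stated rules do not favour the experimental arm overall.** This stands. A reader might infer from the late opening that the 3.0 K bath is made to look safer. The opening rule taken alone can only lower the 3.0 K count, but the closing rules pull the other way: the 3.0 K window is 83 days against 78 and takes in more of the other bath at cross-over. The net direction is not established.

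**Non-serious events are not collected that early anyway.** This also stands, as a limit. Section 6.4.1 and Table 1 footnote 8 collect adverse events from the first Lokelma dose, and serious ones from consent. Taken literally, a non-serious event on Day 1, or on Day 71 in a patient who started on 2.0 K, is never recorded. Nor is a non-serious event at the first 2.0 K session in those patients. Only serious events are then affected by the window. The Table 1 adverse-event row and the 2.0 K definition presuppose earlier collection, so these places must be reconciled. Repairing collection would not repair the window.

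**The loss could be said to be much larger.** A reader might take the reference in 7.2.1 to the 8-week treatment phase to mean no Lokelma in the accommodation weeks. The first dose would then be Day 16 or 86, and 6 + 1 = 7 of 30 sessions (23%) would precede the window. The synopsis and the dispensing row of Table 1 place Lokelma in those weeks, so the document does not support that figure as it stands. The passages must be reconciled.

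**Listings, serious-event reporting and the SAP cover the rest.** In part. All events are listed and safety summaries are descriptive, which limits the harm, but listings do not compare treatments. Section 8.5.6 leaves detail to the SAP yet already fixes this definition.

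**Conclusion.** The asymmetry is real and follows from the protocol's own text: one session in thirty on the 3.0 K bath, the first, can never yield a 3.0 K TEAE. Depending on sequence and on how the tail is read, a switch-day event is left out of the tables or shown under the other bath. A patient with no dose after cross-over contributes nothing to the 3.0 K column.

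The severity is minor. The size rests on three assumptions: that a period begins at the bath switch (Day 1 or 71), that Lokelma starts on the first off-dialysis day, and that the weekly visits keep to Table 1. The effect on non-serious events depends on how 6.4.1 is resolved. Neither a net bias in favour of the experimental treatment nor a 23% loss is shown.

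**What to change.** In 8.5.6, replace the first dose date as the start of the 3.0 K window, and use one rule for both baths: the window opens on the date of the first dialysis session on the assigned bath in that period. Assign an event whose start date is the switch date to the new bath by date alone, because 6.4.3 collects start and stop dates but no onset time. For a patient with no Lokelma dose, name an end date as well, since the present end is tied to the last dose; the last-visit rule already used for 2.0 K would serve.

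Alongside this, reconcile 6.4.1 and Table 1 footnote 8 with the Table 1 adverse-event row and the 2.0 K definition, and reconcile 7.2.1 with the synopsis and Table 1 on the accommodation weeks. The unequal 14-day tails need their own decision.

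The window change costs a short text edit and one programming rule; session dates are known and no new field is needed. The downside is that some events that began on the switch day before the session will be counted under the new bath, on both baths alike.

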## Duration of treatment

Following the screening period’s two confirmatory pre-dialysis  $K^+$  measurements and after meeting study eligibility criteria, patients will be referred to the electrophysiology cardiologist of choice by the site principal investigator where a sub-cutaneous (SQ) continuous cardiac loop recorder will be placed in the left anterior chest wall. Patients will be allowed to accommodate to the loop recorder for 2-weeks before they are randomized (1:1 ratio) to one of two treatment sequences (Sequence A or B, as described above), and start study treatment with 2.0  $K^+$ /2.5 $Ca^{++}$  dialysate bath without potassium binder supplementation or 3.0  $K^+$ /2.5  $Ca^{++}$  dialysate bath with Lokelma supplementation (taken on off-dialysis days). There will be a **2-week** cardiac monitoring blanking period where patients will be allowed to accommodate to the higher  $K^+$  dialysate and the use of Lokelma. Any data recorded by the insertable loop recorder (ILR, LINQ device) during this time period will not be used for any endpoint analysis. During the next **8-week** treatment period (Phase I of the study), patients will undergo continuous cardiac monitoring by the ILR. At the end of Phase I, data will be downloaded from the ILR and a new **2-week** blanking period will begin where patients will “cross-over” to the alternative dialysate bath and will be allowed to equilibrate to the new dialysate. Patients dialyzed for 8 weeks using a 2.0  $K^+$ /2.5 $Ca^{++}$  bath (without potassium binder supplementation) during Phase I will be switched to the 3.0  $K^+$ /2.5  $Ca^{++}$  bath with Lokelma supplementation, and *vice versa*. During the subsequent **8-week** treatment period (Phase II of the study), patients will undergo continuous cardiac monitoring by the ILR. At the conclusion of Phase II, a new cardiac monitoring blanking period will begin and blood sampling will be stopped. The ILR will be removed by the affiliated electrophysiology cardiologist. This process may take an additional 2 weeks. Therefore, for each patient, the planned total study treatment duration will be **20 weeks**, and the total study participation will be approximately **25 weeks**.

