**Table 1 Study Plan and Schedule of Assessments**

Study Period / Visit	Screening	ILR Insertion by EP cardiologist	Baseline/ Randomization	New Dialysate Accommodation Period 1	Treatment Phase 1	Cross-over	New Dialysate Accommodation Period 2	Treatment Phase 2	ILR Removal by EP cardiologist	End of Study	Reference to Protocol Section
Study Week (Wk) [* , ** or ***]	-4 to -3**	-2*	1**	1 & 2**	3 to 10**	11**	11 & 12**	13 to 20**	21-22*	22-23***	
Study Day (D)	-28 to -15	-14	1	1 to 14	15 to 70	71	71 to 84	85 to 140	Between D141 and D155	Within 1 to 14 days after ILR Removal	
Inclusion/exclusion criteria	X		X								3.1, 3.2
Day of the Week			M/T	M/T	M/T	M/T	M/T	M/T			
ILR insertion [7]		X									4.1.9
Randomization to one of two treatment sequences [6]			X								3.5
Study drug dispensed/ returned on 3.0 K+/2.5 Ca++ dialysate group				X	X		X	X			7.2.2
Cardiac Data Loop Recordings					X			X			4.2.2
K+, Ca++ and PO 4 Piccolo POCT promptly before dialysis end) [2]				X	X		X	X			4.2.1

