### **Post-LINQ Device Insertion**

For 2 weeks after LINQ device insertion, patients will be given time to heal and adapt to the device. During this 2-week blanking period, the device will measure continuous cardiac data, but it will not be interrogated and will not be used for analysis. During this blanking period, Medtronic will train study staff on how to interrogate and transmit LINQ device data, which will be sent to the Medtronic Monitoring Service; refer to the data flow shown in Figure 9.

After the 2-week ILR post-insertion recovery period, patients will be randomized to one of two treatment sequences, as described in [Section 3.5](#). The day of randomization will be denoted as Study Day 1 and will also mark the start of Treatment Phase 1.

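### TEAE windows run 14 days past each period's last dose or visit with no stop at cross-over, so AEs around the switch are tabulated under the wrong treatment or under both

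*Protocol*

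**What the plan says.** Section 8.5.6 defines two TEAE windows:

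- **3.0 K+ bath with Lokelma:** from the first dose "up to (and including) 14 days after the last dose date in each of study periods when patients received 3K Bath with Lokelma".
- **2.0 K+ bath without Lokelma:** "on or after the first visit date and up to (and including) 14 days after the last visit date in each of study periods".

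The same section restricts the AE tables to TEAEs and presents them by treatment group and study period. It has no rule for an AE that falls in both windows, and none that ends a window when the other treatment begins.

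On the switch itself, footnote [6] of Table 1 states: "Crossover occurs on the same day as Week 11 of the new Dialysate Accommodate Period 2". The synopsis (Duration of treatment) says that patients cross over "to the alternative dialysate bath and will be allowed to equilibrate to the new dialysate". It describes the first accommodation fortnight as a time to get used to the higher-potassium "dialysate and the use of Lokelma". The Table 1 row "Study drug dispensed/ returned on 3.0 K+/2.5 Ca++ dialysate group" is marked for both accommodation periods as well as both treatment phases.

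**The concern.** A 14-day tail works where nothing else is given during those 14 days: in a parallel-group trial, or in a cross-over with an untreated wash-out. Here the fortnight after the first treatment is the first fortnight of the second. Section 8.5.1 refers to a wash-out period, but the schedule has no off-treatment days.

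Safety Objective #3 compares AE frequencies between the two treatments, and the window decides which column an AE enters. The affected days are those on which the bath changes and Lokelma starts or stops, when an AE related to the change might be expected. The tails also hang on different anchors (last dose against last visit), so they need not be equally long.

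**Working it through.** **Inputs**

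- Table 1: accommodation 1 is Days 1-14, Phase 1 is Days 15-70, accommodation 2 is Days 71-84, Phase 2 is Days 85-140. Visits are weekly on the first dialysis day after the long interval, so Week 10 is Day 64 and Week 11 is Day 71.
- Section 7.2.1: dosing is on the four off-dialysis days. On either dialysis schedule these are days 2, 4, 6 and 7 of the study week. The last period-1 dose is therefore Day 63 + 7 = 70, and the first period-2 dose is Day 70 + 2 = 72.
- Section 8.5.6: the tail is 14 days.

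**Is there a gap?** 2 + 8 + 2 + 8 = 20 weeks = 140 days. This reproduces the synopsis's 20 weeks of treatment and fills Table 1 from Day 1 to Day 140. No untreated day is left.

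**Overlap** is the span from the opening of the new window to the old anchor + 14. Sequences are named by their first treatment because Table 4 reverses the A/B labels used elsewhere.

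| Sequence | Old window ends | New window opens | Counted twice |
|---|---|---|---|
| 3.0 K+ first | 70 + 14 = Day 84 | Day 71 (visit) | Days 71-84: 14 days |
| 2.0 K+ first, last visit Week 10 | 64 + 14 = Day 78 | Day 72 (dose) | Days 72-78: 7 days |
| 2.0 K+ first, end-of-week vitals session counts as a visit (Day 68) | 68 + 14 = Day 82 | Day 72 | Days 72-82: 11 days |
| 2.0 K+ first, Day 71 counts as last visit | 71 + 14 = Day 85 | Day 72 | Days 72-85: 14 days |

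As a share of a 70-day period this is 7/70 = 10% to 14/70 = 20%. It shrinks if Lokelma is stopped before Day 70.

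**If a study period means only the 8-week phase.** Period 2 then opens on Day 85 (2.0 K+ visit) or Day 86 (first Lokelma dose in Phase 2), and no day is counted twice. But in 3.0 K+ first patients, Days 71-84 are spent on the 2.0 K+ bath and are tabulated only under 3.0 K+. In 2.0 K+ first patients with a Week 10 last visit, AEs on the 3.0 K+ bath on Days 71-78 are tabulated only under 2.0 K+, and Days 79-85 fall in neither window.

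**Illustration of the effect on counts.** Assume equal sequence sizes, hazard 1 per day on 2.0 K+ or off study, and hazard R on 3.0 K+ with Lokelma.

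- *Complete AE collection, 14-day tails:* 3.0 K+ count = 2(70R + 14); 2.0 K+ count = (70 + 14R) + (70 + 14). R = 2 gives 308/182 = 1.69.
- *Complete collection, 2.0 K+ tail reaching only 8 days past each period's end (Week 10 and Week 20 visits taken as last):* 2.0 K+ count = (70 + 8R) + (70 + 8). R = 2 gives 308/164 = 1.88; R = 1 gives 168/156 = 1.08.
- *Collection as section 6.4.1 and Table 1 footnote [8] state it:* non-serious AEs are collected only from the first Lokelma dose, so the first 70 days of 2.0 K+ first patients drop out. With 14-day tails the 2.0 K+ count = 84 + 14R. R = 2 gives 308/112 = 2.75; R = 1 gives 168/98 = 1.71.

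The last case is driven mainly by the collection rule. Closing the period-1 windows at cross-over would still leave (140 + 14)/84 = 1.83 at R = 1.

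**The case against.** **Study period may mean the 8-week phase.** Section 8.3.3 with Table 4 sets the reporting periods as Treatment Phase-1 and Phase-2, and section 7.2.1 attaches dosing to the 8-week phase. This reading has support and removes the double count. It conflicts with the text after device insertion in section 4.1.9, "The day of randomization will be denoted as Study Day 1 and will also mark the start of Treatment Phase 1", and with Lokelma being dispensed during accommodation. Those passages need to be reconciled. The reading does not rescue the rule, because it replaces double counting with attribution to the wrong treatment.

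**Details are left to the SAP.** Section 8.5.6 defers full safety details, but it states the window itself. A SAP that cut the window at cross-over would depart from the protocol.

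**Safety is descriptive.** This stands, and it limits the severity. No test or decision rule rests on the AE tables, no AE rate ratio is planned, and the primary endpoint is untouched. Per-patient listings and collected onset dates allow AEs to be reassigned later.

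**Stronger readings.** A reader might infer that the overlap pulls the treatments together by a known amount, for instance a true ratio of 2.0 shown as 1.69. The protocol does not support that as a net effect. The figure needs constant hazards and AE collection from Day 1 in both sequences, so it applies at most to SAEs, which are collected from consent. For non-serious AEs the collection rule can push the tabulated ratio the other way, and unequal tails can produce a small difference where none exists. A reader might also infer two weeks of double counting for everyone; that is exact only for 3.0 K+ first patients.

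**Conclusion.** The point holds as a should-fix. Followed as written, 8.5.6 puts AEs with onset shortly after cross-over under both treatments: 14 days for 3.0 K+ first patients, and 7 to 14 days for 2.0 K+ first patients depending on which visit is the last one on 2.0 K+. On the narrower meaning of study period, they go under the treatment already stopped. These figures assume dosing through Day 70, weekly visits on the Table 1 days, and Lokelma starting in the accommodation weeks as the synopsis and Table 1 indicate. The by-treatment AE tables are misattributed around the switch on either reading. The size and direction of the net bias cannot be settled from the protocol.

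**What to change.** In 8.5.6:

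- End the period-1 TEAE window for both treatments at the start of the period-2 treatment (the Week 11 cross-over). The overlap then becomes 0 days in both sequences.
- Assign each AE to the treatment in force at onset.
- Keep the 14-day tail only after period 2 or early withdrawal, on one common anchor date for both treatments.
- Show AEs with onset in Weeks 11-12 in a separate row.
- State whether a study period includes its accommodation weeks.

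The cost is a short change to 8.5.6, carried into the SAP. No new data are needed, because section 6.4.3 already collects AE start dates. The downside is that a delayed effect of the first treatment is attributed to the second; the separate row keeps it visible.

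Reconcile separately the start of non-serious AE collection (first Lokelma dose, section 6.4.1 and Table 1 footnote [8]) with a 2.0 K+ window that opens at the first visit. Changing the windows does not cure that imbalance.

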### **3.9 Discontinuation of Investigational Product**

Patients may be discontinued from investigational product (IP) in the following situations:

- Patient decision. The participant is at any time free to discontinue treatment, without prejudice to further treatment;
- Incorrectly randomized participant where violation of the inclusion/exclusion criteria would put the participant at undue risk;
- Adverse event for which the investigator judges continued treatment may put the participant at undue risk;
- Pregnancy;
- Development of any of the following study-specific criteria for discontinuation:
  - Permanent atrial fibrillation, as determined by echocardiogram or cardiology assessment;

- Requiring for permanent placement of a cardiac pacemaker or AICD;
  - Refractory hyperkalemia ( $K^+ > 6.5$  mEq/L) while on 15 grams 4 days per week of Lokelma;
  - Hypokalemic event (defined as pre-dialysis  $K^+$  level of  $< 3.5$  mEq/L): Patients experiencing a minimum of two (2) hypokalemic events while taking Lokelma will have their Lokelma adjusted or discontinued at the discretion of the site PI;
  - Renal transplant.
- Severe non-compliance with the study protocol.

Note: patients wishing to remain in the study on treatment despite developing an adverse event may do so at the site PI's discretion, unless they remain hyperkalemic with  $K^+ > 6.5$  mEq/L after a long inter-dialytic interval (LIDI) for two (2) consecutive weeks.

Regardless of the reason for discontinuation, all reasons for discontinuation of study treatment must be documented in the electronic case report form (eCRF).

If the patient is discontinued from investigational product, the scheduled study visits, data collection and procedures should continue according to the study protocol until study completion, unless the patient withdraws consent for any further study procedures and follow-up. The approach taken should be documented in the eCRF.

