### **6.4 Recording of adverse events**

#### **6.4.1 Time period for collection of adverse events**

Adverse events will be collected from the time of first dose of Lokelma®, throughout the treatment and post-treatment follow-up period, up to the last study visit.

SAEs will be reported from the time the patient signed the Informed Consent Form.

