## 6.9 Management of IP-related Toxicities / Dose Reductions

The study drug (Lokelma) will be titrated from 5.0 grams per day (4 days/week) up to a maximum of 15.0 grams per day (4 days/week), to maintain  $K^+$  within the desired target range (between 4.0 and 5.5 mEq/L). potassium levels will be regularly monitored, and the study drug dose adjusted based on the potassium levels (i.e., increased [up to a maximum of 15.0 grams/day] if potassium is  $>5.5$  mEq/L, or decreased if potassium is  $<4.0$  mEq/L).

As described in [Section 3.9](#), the study drug will be permanently discontinued in case the patient develops any of the following IP-related events:

- Two (2) or more hypokalemic events (defined as pre-dialysis  $K^+$  level of  $<3.5$  mEq/L);  $<$

Refer to [Section 3.9](#) for further details on events requiring permanent discontinuation of the study drug.

Safety protocols for the management of intra-dialytic events are provided in [Section 5.3](#).

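### The adverse-event window follows Lokelma dosing in the 3.0 K period but visits in the 2.0 K period, so events well after an early drug stop leave the 3.0 K tables only

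*Protocol*

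**What the plan says.** Section 8.5.6 of the protocol defines treatment-emergent events by start date, with a different closing rule for each treatment:

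- 3.0 K bath with Lokelma: from the first dose "up to (and including) 14 days after the last dose date in each of study periods when patients received 3K Bath with Lokelma".
- 2.0 K bath: "on or after the first visit date and up to (and including) 14 days after the last visit date in each of study periods".

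It then states: "Only TEAEs will be included in table summaries". Those tables cover AEs, SAEs, withdrawals and fatal events: "AEs that led to death, and the number of such events, will be summarised by SOC, PT, and treatment group and study period". The same section puts all AEs and SAEs into per-patient listings.

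Stopping Lokelma does not by itself end participation. Under section 3.9, unless consent for further follow-up is withdrawn, "the scheduled study visits, data collection and procedures should continue according to the study protocol until study completion". Section 6.4.1 collects AEs "throughout the treatment and post-treatment follow-up period, up to the last study visit", starting at the first Lokelma dose. SAEs are reported from consent.

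**The concern.** The experimental treatment is a bath plus a drug, and Safety Objective #3 (section 2.3) compares it with standard treatment on AEs, SAEs and withdrawals due to AEs. The 3.0 K window follows only the drug. When Lokelma stops early in a patient who stays in the study, the window closes 14 days later although the period and the data collection go on. Nothing in the 2.0 K period can close the window this way.

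The loss is unlikely to be random. Section 3.9 lists adverse events, permanent atrial fibrillation, refractory hyperkalemia and repeated hypokalemia among the reasons to stop the drug. The untabulated days would then belong to patients already in difficulty. At stake is whether the between-treatment safety tables compare the two treatments over the same follow-up.

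**Working it through.** The protocol states no figure to reproduce here, since the point rests on a definition. The check works out both windows in days.

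**Inputs**
- Period length: 2 weeks of accommodation plus 8 weeks of treatment = 70 days (Table 1: Days 1–70; cross-over on Day 71).
- Window ends: last dose + 14 days (3.0 K) and last visit + 14 days (2.0 K), from section 8.5.6.
- L = day of last Lokelma dose, and f = share of patients who stop early, stay in the study and do not re-start. The protocol gives neither. Assumed: L = 21, 35 or 56; f = 5% to 30%.

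**One patient.** The 3.0 K window closes on Day L + 14. Taking Day 70 as the end of the period, the 2.0 K window closes on Day 70 + 14 = 84.

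| Last dose (L) | 3.0 K window closes | Period days lost, of 70 | Window days lost, of 84 |
|---|---|---|---|
| Day 21 | Day 35 | 70 − 35 = 35 (50%) | 84 − 35 = 49 (58%) |
| Day 35 | Day 49 | 70 − 49 = 21 (30%) | 84 − 49 = 35 (42%) |
| Day 56 | Day 70 | 0 | 84 − 70 = 14 (17%) |

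**All patients, equal true event rates.** Apparent 3.0 K/2.0 K ratio = 1 − f × (70 − L)/84.
- Smallest effect: f = 5%, L = 56: 1 − 0.05 × 14/84 = 0.992.
- Middle: f = 10%, L = 21: 1 − 0.10 × 49/84 = 0.942.
- Largest: f = 30%, L = 21: 1 − 0.30 × 49/84 = 0.825.

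Counting only the 70 period days, the range is 1.00 (L = 56, nothing lost) to 1 − 0.30 × 35/70 = 0.85.

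**If risk is higher after stopping.** As an illustration, assume f = 20%, L = 21 and four times the event rate after the last dose. Total 3.0 K events are proportional to 0.8 × 84 + 0.2 × (21 + 4 × 63) = 121.8. Those lost are 0.2 × 4 × 49 = 39.2, or 32%.

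**Deaths.** Section 1.1 gives an annual death rate of about 23.7%, a hazard of −ln(0.763) = 0.270 per year. Expected deaths falling in the lost days, among 88 patients:
- f = 5%, 35 days lost: 4.4 × (1 − exp(−0.270 × 35/365)) ≈ 0.1.
- f = 10%, 49 days lost: 8.8 × (1 − exp(−0.270 × 49/365)) ≈ 0.3.
- f = 30%, 49 days lost: 26.4 × 0.036 ≈ 0.9.

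These are upper figures at that background rate, because a death leaves the table only if the fatal AE also starts after the window closes.

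**After the change.** If both windows follow the period, they close together and the ratio under equal true rates is 1.00 for any f.

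**The case against.** Several points on the other side stand.

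- **Nothing vanishes from the report.** The events stay in the listings, and section 6.5 requires every SAE from consent to be reported. A reader might infer that deaths are concealed. The text does not support that: what is lost is the tabulated comparison, and only for fatal AEs with a late start date.
- **Some early stops are not affected.** It is tempting to cite the patient who is still hyperkalemic after a week on the top dose. Section 7.2.1 withdraws such a patient from the study, so a visit-based window would also close early. Section 3.9 instead lists refractory hyperkalemia as a reason to stop the drug, with visits continuing. The two sections conflict, so this case cannot carry the point.
- **Hypokalemia need not end dosing.** Section 6.9 says that "the study drug will be permanently discontinued in case the patient develops any of the following IP-related events" and names two or more low pre-dialysis values. Sections 3.9 and 5.3.1 leave adjusting or stopping to the site investigator, and section 3.9.1 allows a re-start, which moves the last dose date later.
- **Net direction.** A reader might infer that the whole AE comparison leans towards the experimental treatment. Section 6.4.1 and Table 1 note 8 collect non-serious AEs only from the first Lokelma dose. Read literally, the half of patients (44 of 88) who receive 2.0 K first have none collected in that period. This under-counts the 2.0 K column and could outweigh the window effect.
- **Weight.** A last-dose window is a common convention, the safety analyses are descriptive, no efficacy test is touched, and the SAP may add detail.

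The listings do not answer a comparative objective, however, and the unequal definition is stated in the protocol rather than left open. Stops for AEs, permanent atrial fibrillation or patient choice remain, and under section 3.9 those patients stay in follow-up. For SAEs, collected from consent, the late start of non-serious AE collection gives no offset.

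**Conclusion.** The point holds in a limited form. For patients who stop Lokelma early, stay in the study and do not re-start, section 8.5.6 omits from the 3.0 K tables any event starting more than 14 days after the last dose, and applies no equivalent cut-off to 2.0 K. A last dose on Day 21 costs 35 of 70 period days for that patient. Overall, the apparent ratio under equal true rates is about 0.99 to 0.83 for an assumed 5% to 30% stopping between Day 56 and Day 21. It is further from 1 if risk rises after stopping.

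The bias favours the experimental treatment for SAEs and fatal events. For non-serious AEs the net direction cannot be determined from the protocol.

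These figures assume that the stopped patient's later time belongs to the 3.0 K period. The protocol does not say which bath or column applies after a drug stop. It is a flaw in the comparative safety tables, not in any efficacy inference, and should be settled before database lock.

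**What to change.** In section 8.5.6, or in the SAP with a matching protocol correction:

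1. For the between-treatment tables, use one window for both treatments: from the first visit of the assigned period to the end of that period, whether or not Lokelma was stopped. Cut it at cross-over, because a 14-day extension from the first period would run into the other treatment. Apply the same follow-up extension to both treatments after the last period.
2. Keep last dose + 14 days only for a supplementary on-drug table.
3. In section 6.4.1 and Table 1 note 8, use the same starting point for AE collection in both sequences.
4. Reconcile sections 3.9, 5.3.1, 6.9 and 7.2.1 on when Lokelma is stopped and whether those patients remain in the study, and state which treatment column their later events belong to.

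Items 1 and 2 take about two sentences and no new data, since sections 3.9 and 6.4.1 already provide for collection after a drug stop. Item 3 requires non-serious AEs to be recorded in a first 2.0 K period, for which Table 1 already has the visits. The small downside is that some AEs counted under 3.0 K will have occurred off drug, which the supplementary table makes visible.
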